5.0 Analysis Populations and Important Subgroups

5.1 Analysis Population

The Intent-to-Treat (ITT) Population will be used for the efficacy analyses. The ITT Population is defined as all subjects who are randomized at Baseline.

The following populations will be used for safety analysis:

- The Safety Population is defined as all subjects who are randomized at Baseline (ITT population) and received at least one dose of study drug. The Safety Population will be used to perform the 52-week head-to-head safety analysis between the two treatment groups.
- The All Risankizumab Treated (All_RZB) Population is defined as subjects who receive at least one dose of risankizumab in the study. The All_RZB Population will be used to perform a comprehensive safety summary for risankizumab.

In order to evaluate the impact of major protocol violations on the primary efficacy endpoints, additional sensitivity analyses will be performed on a Per-protocol Population, which excludes subjects with major protocol deviations that potentially affect the primary efficacy endpoints. The criteria for exclusion of subjects from the Per-protocol Population will be fully defined in the classification plan and the exclusion of subjects from the Per-protocol Population for the analysis will be finalized before the database lock.

5.2 Subgroup

Subgroup analyses will be performed for the primary endpoints by demographics and baseline characteristics as described in detail below (Section 6.5).

6.0 Efficacy Analysis**6.1 General Considerations**

The Primary Analysis for all efficacy endpoints pertaining to Period A will be conducted after all continuing subjects have completed Week 16 and all data pertaining to Period A are cleaned and a database lock will occur to enable the analysis. This is the one and final efficacy analysis for Period A. The results will be included in an interim clinical study report (CSR) to support the efficacy and safety evaluation in the initial 16 weeks of treatment.

The Primary Analysis for all efficacy endpoints in Period B will be conducted after all continuing subjects have completed Week 52 and all data pertaining to Week 52 are cleaned and when a database lock will occur to enable the analysis.

The efficacy assessors will remain blinded for the duration of the entire study.

The efficacy analysis will be conducted in the ITT Population and Per-protocol Population. The ITT Population will be analyzed by treatment group as randomized. For the Per-protocol Population, subjects will be analyzed as randomized.

Comparison of the primary endpoints will be made between risankizumab group and secukinumab group using the Cochran-Mantel-Haenszel test adjusting for stratification by weight (≤ 100 kg vs. > 100 kg) and prior systemic biologic use for psoriasis. For the primary analysis, Non-Responder Imputation (NRI) will be used. The analysis will be repeated using last observation carried forward (LOCF) and Multiple Imputation (MI).

Categorical variables will be analyzed using Cochran-Mantel-Haenszel (CMH) test, stratified by weight (≤ 100 kg vs. > 100 kg) and prior systemic biologic use for psoriasis.

Continuous variables will be analyzed using ANCOVA method, with treatment, pooled center, and Baseline values in the model.

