5.8 Randomization/Drug Assignment

Each subject will be assigned a unique identification number by the IRT at the screening visit. For subjects who rescreen, the screening number assigned by the IRT at the initial screening visit should be used. Subjects may only be rescreened one time. The IRT will assign a randomization number that will encode the subject's treatment group assignment according to the randomization schedule generated by the statistics department at AbbVie. Subjects will be randomized in a 1:1 ratio to one of two treatment groups:

- Group 1: Risankizumab 150 mg (N = 155)
- Group 2: Secukinumab 300 mg (N = 155)

The randomization will be stratified by weight (≤ 100 kg vs. > 100 kg) and prior systemic biologic for psoriasis.

This is an open-label study; however, the efficacy assessor will remain blinded to each subject's treatment, clinical laboratory results, and all subject safety data during the course of the study.

In the event of a medical emergency in which the Investigator believes that knowledge of study drug treatment is required for the efficacy assessor, reasonable efforts must be made to contact the AbbVie Emergency Contact.

The date and reason that the efficacy assessor's blind was broken must be recorded in the source documentation and eCRF, as applicable.

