4.2.2 Variables Used for Stratification at Randomization

The randomization will be stratified by weight (≤ 100 kg vs. > 100 kg) and prior systemic biologic for psoriasis (0 vs. ≥ 1).

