4.3.3 Exploratory Efficacy Endpoint

The exploratory endpoints listed below will be analyzed for all visits in which the assessments are performed (other than those already included as primary or secondary endpoints):

- Proportion of subjects achieving $\geq 75\%/90\%/100\%$ reduction from baseline in PASI score (PASI 75/90/100);
- Proportion of subjects achieving sPGA score of clear (0) or almost clear (0 or 1);

- Change and percent change from baseline in PASI and body surface area (BSA).

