4.6 Multiplicity Testing Procedures for Type-I Error Control

The statistical comparisons for the two primary efficacy variables and the three ranked secondary variables will be carried out using graphical procedures as shown in [Figure 2](#).

The 2 primary hypotheses are:

- H1: Risankizumab is not different from secukinumab in achieving a PASI 90 response at Week 52.

- H2: Risankizumab is inferior to secukinumab by 12% in achieving a PASI 90 response at Week 16.

[figure not shown]
The second null hypothesis (H2) will be tested with a two-sided type I error 0.0375. If the result is significant ($p\text{-value} < 0.0375$), then the 0.0375 will be passed to the first null hypothesis (H1), which will be tested with a two-sided type I error 0.05. On the other hand, if the result of H2 is not significant ($p\text{-value} \geq 0.0375$), then H1 will be tested with a two-sided type I error 0.0125.

The multiplicity-controlled, ranked key secondary hypotheses are:

- H3: Risankizumab is not different from secukinumab in achieving a PASI 100 response at Week 52.
- H4: Risankizumab is not different from secukinumab in achieving an sPGA 0 or 1 at Week 52.
- H5: Risankizumab is not different from secukinumab in achieving a PASI 75 response at Week 52.

The three null hypotheses of secondary endpoints (H3, H4, and H5) will be tested in a sequential order with initial two-sided type I error of H3 same as that in H1, only when H1 is significant at its two-sided alpha level. The statistically significant results for the comparison in the higher rank of secondary endpoints are necessary to initiate the testing of the next comparison in the lower rank.

The details of using graphical procedures to control family wise type-I error could be found in Bretz, F, Maurer, W, Brannath, W, & Posch, M (2009).³

Figure 2. Graphical Approach for Type-I Error Control

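### The ANCOVA for the exploratory continuous endpoints leaves out both randomization stratification factors, so its standard errors are too large if those factors are prognostic beyond Baseline value and center

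*SAP*

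**What the plan says.** SAP 4.2.2 states: "The randomization will be stratified by weight", with a cut at 100 kg. The second factor is prior systemic biologic use, none against at least one. Protocol 5.8 names the same pair, weight "and prior systemic biologic for psoriasis". Center is not listed as a stratification factor in either place.

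SAP 6.1 carries both factors into the binary analyses: "Categorical variables will be analyzed using Cochran-Mantel-Haenszel (CMH) test, stratified by weight" and by prior biologic use. The next sentence gives the model for everything continuous: "Continuous variables will be analyzed using ANCOVA method, with treatment, pooled center, and Baseline values in the model". Neither stratification factor is in it.

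The continuous efficacy endpoints are absolute and percent change in PASI and BSA. SAP 4.3.3 classes them as exploratory: "The exploratory endpoints listed below will be analyzed for all visits in which the assessments are performed". They are outside the alpha-controlled family, which SAP 4.6 limits as follows: "The statistical comparisons for the two primary efficacy variables and the three ranked secondary variables will be carried out using graphical procedures". Protocol 7.3 gives no model for continuous endpoints, and nothing else in the two documents adds the stratification factors to the ANCOVA.

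**The concern.** Stratified allocation forces near balance on weight and prior biologic use. If either factor predicts the outcome, that balance reduces the true sampling variability of the treatment difference. A model that omits the factors does not register this reduction: their variance stays in the residual, and the standard error is computed as though allocation had been unstratified. Reported intervals are then wider than the design warrants.

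The SAP gives no reason for handling the two endpoint types differently. The continuous model adjusts for center, on which randomization is not stratified, and leaves out the two factors on which it is.

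The stakes are limited to how precisely the PASI and BSA change results are reported, at every visit where they are analyzed.

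**Working it through.** **The plan's own figures.** The documents give no SD, effect size or standard error for the continuous endpoints, so there is nothing to reproduce for them directly. The stated power for the two primary endpoints (SAP 4.4, 155 per arm) does reproduce:

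- Week 52 superiority, 81.3% vs 60.6%, two-sided alpha 0.0125: 94.0%, against a stated figure of more than 90%.
- Week 16 non-inferiority, 75.1% vs 69.7%, margin 12 points, one-sided alpha 0.0375/2 = 0.01875: 91.2% with unpooled variance and 91.0% with the Farrington-Manning variance, against a stated 90%.

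Both endpoints are binary and analyzed by CMH, so the ANCOVA does not bear on them.

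**Analytic size of the effect.** Let R² be the share of residual variance, after Baseline value and center, that the two factors explain. Under stratified 1:1 allocation the true variance of the treatment difference is proportional to (1 − R²), while the variance reported by the model without the factors is proportional to 1. Hence

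- reported SE / true SE ≈ 1/√(1 − R²)
- actual size of a nominal two-sided 5% test ≈ 2 × [1 − Φ(1.96/√(1 − R²))]

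| R² (assumed) | SE overstated by | Actual size of 5% test |
|---|---|---|
| 0% | 1/√1.00 − 1 = 0% | 5.0% |
| 2% | 1/√0.98 − 1 = 1.0% | 4.8% |
| 5% | 1/√0.95 − 1 = 2.6% | 4.4% |
| 10% | 1/√0.90 − 1 = 5.4% | 3.9% |
| 20% | 1/√0.80 − 1 = 11.8% | 2.8% |

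**Simulation with pooled center in both models.** The 310 subjects come from SAP 4.4. Everything else is assumed: permuted blocks of 4 within the four strata, 30% above 100 kg, 40% with a prior biologic, 10 pooled centers explaining 5% of variance, no treatment effect. There were 100,000 runs per case, so the Monte Carlo error of a 5% size is √(0.05 × 0.95/100,000) ≈ 0.07 points.

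| R² | Model | Mean reported SE | True SD | SE/SD | Size | Mean 95% CI half-width |
|---|---|---|---|---|---|---|
| 0% | SAP | 0.1154 | 0.1156 | 0.999 | 5.03% | 0.2271 |
| 0% | with factors | 0.1154 | 0.1156 | 0.999 | 5.03% | 0.2271 |
| 2% | SAP | 0.1154 | 0.1145 | 1.008 | 4.82% | 0.2271 |
| 2% | with factors | 0.1143 | 0.1144 | 0.999 | 5.03% | 0.2248 |
| 5% | SAP | 0.1154 | 0.1128 | 1.023 | 4.51% | 0.2271 |
| 5% | with factors | 0.1125 | 0.1126 | 0.999 | 5.03% | 0.2214 |
| 10% | SAP | 0.1154 | 0.1099 | 1.050 | 3.96% | 0.2271 |
| 10% | with factors | 0.1095 | 0.1096 | 0.999 | 5.03% | 0.2155 |

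Two things follow. The true SD is nearly the same under both models, so the loss is in reported precision rather than true precision. And adding the factors narrows the interval by 1 − 0.2248/0.2271 = 1.0%, 1 − 0.2214/0.2271 = 2.5% and 1 − 0.2155/0.2271 = 5.1% at R² of 2%, 5% and 10%.

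**Sensitivity to the assumed inputs.** A second simulation used 15 pooled centers, 35% with a prior biologic and 4,000 runs per case. At R² of 5%, 10% and 20% the SAP model gave SE/SD of 1.03, 1.04 and 1.11, with size 4.5%, 4.1% and 3.0%. With the factors added, SE/SD was 1.01, 0.99 and 1.00, with size 5.2%, 5.5% and 5.1%. The direction is the same, and the differences from the table are of the order expected with that number of runs.

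**The case against.** **Nothing the trial decides on moves.** The affected endpoints carry no alpha, have no decision threshold and were not powered. The error is conservative, and Protocol 7.3 requires adjustment for the stratification factors only for the primary endpoint, so the SAP breaks no stated rule. All of this stands, and it is why the point is minor. It does not make the reported interval right.

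**The size is unknown.** The documents do not show that either factor is prognostic for PASI or BSA change once Baseline value and center are in the model, and the range shown includes zero. The strata shares, block size and number of pooled centers are also assumptions: the Protocol synopsis lists 80 sites, and neither document says how they are pooled. This stands too. The choice to stratify on these factors and to adjust every CMH test for them makes prognostic value plausible, not proven.

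**The details may be elsewhere.** Protocol 7.1 and SAP 3.0 defer further detail to a SAP supplement, which was not available. It might add terms. But SAP 6.1 lists the model terms explicitly, and a reader is entitled to take that list as the model.

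**Main effects may not be enough.** Blocking within four cells also balances the weight-by-biologic interaction. If the whole stratum effect were a pure interaction explaining 10% of residual variance, adding the two main effects would not help: simulated SE/SD was about 1.05 to 1.06 with or without them. The restored 5% size in the working therefore assumes additive stratum effects. A pure interaction is an extreme case, and even then the amended model does no worse than the planned one.

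**Conclusion.** The concern holds, as a minor point. The ANCOVA in SAP 6.1 omits both factors on which randomization is stratified. If they are prognostic beyond Baseline value and center, standard errors for the PASI and BSA change endpoints are overstated, by about 1% to 5% for an assumed R² of 2% to 10%. If they are not, there is no effect. The treatment estimate is unbiased and false-positive risk does not rise.

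This rests on an assumed R², on reading Baseline values as the baseline of the variable being analyzed, and on the supplement not adding the terms.

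**What to change.** Amend the ANCOVA sentence in SAP 6.1 so that the model contains treatment, pooled center, the Baseline value, weight stratum (≤ 100 kg or > 100 kg) and prior systemic biologic use (0 or ≥ 1). If the supplement already includes these terms, the SAP should say so. Whether to keep pooled center is a separate question and need not be settled here.

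The cost is one sentence. Both variables are already recorded for randomization and used in the CMH tests. With 10 pooled centers assumed, residual degrees of freedom fall from 310 − 12 = 298 to 296. If the factors turn out not to be prognostic, the mean 95% CI half-width is unchanged (0.2271 against 0.2271 SD units). A single four-level stratum term would also cover the interaction case, for three degrees of freedom instead of two.

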6.2 Primary Efficacy Analysis

The two primary endpoints are:

- Proportion of subjects achieving a PASI 90 response at Week 52; superiority of risankizumab vs secukinumab.
- Proportion of subjects achieving a PASI 90 response at Week 16; non-inferiority of risankizumab vs. secukinumab with non-inferiority margin of 12%.

6.3 Secondary Efficacy Analysis

The multiplicity-controlled, ranked key secondary endpoints are:

- Proportion of subjects achieving a PASI 100 response at Week 52; superiority of risankizumab vs. secukinumab;
- Proportion of subjects achieving an sPGA 0 or 1 at Week 52; superiority of risankizumab vs. secukinumab;
- Proportion of subjects achieving a PASI 75 response at Week 52; superiority of risankizumab vs. secukinumab.

6.4 Other Efficacy Analysis

Other efficacy endpoints include PASI 75/90/100, sPGA of clear or almost clear (0 or 1), change and percent change from baseline in PASI 75/90/100 and body surface area (BSA), except the ones that already included in the primary and secondary endpoints at all visits.

6.5 Efficacy Subgroup Analysis

To evaluate the consistency of the efficacy across demographic and other baseline characteristics, summaries and analyses will be performed for selected subgroups for the primary efficacy variables.

Subgroup analyses will be performed on the primary endpoints using the following subgroups:

- Age group (< 40 years, \geq 40);
- Sex (male, female);
- Race (white, non-white);
- Smoking (current, ex or never)
- BMI (normal: < 25, over weight: \geq 25 – < 30, obese: \geq 30);
- Baseline PASI score (by median);
- Baseline sPGA (3, 4)
- Psoriatic arthritis (yes, no)
- Prior biologic treatment (0, \geq 1)

7.0 Safety Analysis

7.1 General Consideration

Safety analyses will include adverse events, laboratory, vital sign measurements and ECG parameter. Safety summaries will be provided using the safety populations.

The Safety Population will be analyzed as treated, based on the actual treatment received at the randomization visit.

Safety analysis in the All_RZB Population will be performed upon study completion.

7.2 Analysis of Adverse Events

A treatment-emergent AE (TEAE) among the Safety Population is defined as an event with onset or worsening on or after the first dose of study drug until the minimal of (i) 140 days following the last pre-Week 52 dose of risankizumab or secukinumab and (ii) the additional dose on or after Week 52.

A TEAE among the All_RZB Population is defined as an event with onset or worsening on or after the first dose of risankizumab until 140 days following the last dose of risankizumab throughout the study.

All safety analyses will be performed in the safety populations. Pre-treatment AEs will be summarized separately.

Safety summaries will also be provided among the All_RZB Population upon study completion.

All treatment-emergent adverse events (TEAEs), serious adverse events (SAEs), AEs leading to discontinuation, and Areas of Safety Interest (ASI) will be analyzed during the study. The number and percentages of subjects experiencing TEAE will be tabulated using the Medical Dictionary for Drug Regulatory Activities (MedDRA®) system organ class and preferred term. Summaries (including percentages and event per 100 patient-years) of SAEs, deaths, AEs leading to discontinuation, and Areas of Safety Interest will be provided as well.

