4.2 Study Design

4.2.1 Study Design and Design Diagram

This is a Phase 3, global, multicenter, randomized, open-label, efficacy assessor-blinded, active comparator study examining the effect of 150 mg risankizumab versus 300 mg secukinumab in patients with moderate to severe plaque psoriasis who are candidates for systemic therapy. The study is designed to randomize approximately 310 subjects (155 subjects/arm).

[figure not shown]
The study duration will be up to 88 weeks. The study comprises a 30-day Screening Period, a 52-week open-label study period and a 16-week follow-up period. The follow-up period consists of a follow-up phone call 20 weeks after the last dose of study drug. Subjects in France who were randomized to risankizumab will have two additional dosing

visits at Week 52 and Week 64 and a follow-up phone call 20 weeks after the last study drug dose.

For ease of description, Period A refers to Week 0 – 16, and Period B refers to the rest of the study.

Eligible subjects will be randomized to receive risankizumab or secukinumab in a 1:1 ratio as shown below in [Figure 1](#):

- **Treatment A** (risankizumab SC injection): 2 injections of risankizumab 75 mg (150 mg total dosage) received subcutaneously at Weeks 0, 4, and every 12 weeks (q12w) thereafter until at Week 40. Subjects in France who were randomized to risankizumab will have two additional dosing visits at Week 52 and Week 64.
- **Treatment B** (secukinumab SC injection): 2 injections of secukinumab 150 mg (300 mg total dosage) received subcutaneously at Weeks 0, 1, 2, 3, 4, and every 4 weeks (q4w) thereafter until the last dose at Week 48.

Figure 1. Study Schematic**Risankizumab vs. Secukinumab (M16-766)**

The primary analysis for Period A will be performed when the last subject completes the Week 16 visit. There will not be a modification to trial conduct based on the results of the analysis. Efficacy assessors will remain blinded for the duration of the study.

The Primary Analysis for all efficacy endpoints in Period B will be conducted after all continuing subjects have completed Week 52 and all data pertaining to Week 52 are cleaned and when a database lock will occur to enable the analysis.

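### For subjects who complete dosing, the TEAE window runs to Week 68 on secukinumab but Week 60 on risankizumab, so crude TEAE percentages could read modestly higher on secukinumab

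*SAP*

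**What the plan says.** SAP 7.2 (Analysis of Adverse Events) starts the Safety Population TEAE window at the first dose and ends it at the smaller of (i) "140 days following the last pre-Week 52 dose of risankizumab or secukinumab and (ii) the additional dose on or after Week 52". Protocol 7.4 (Statistical Analyses for Safety) also uses 140 days after the last dose, and Appendix D, footnote i, collects adverse events over the same 140 days.

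SAP 4.2.1 sets the dosing. Risankizumab is given at Weeks 0 and 4 and "every 12 weeks (q12w) thereafter until at Week 40", with extra doses at Weeks 52 and 64 in France only. Secukinumab is given "every 4 weeks (q4w) thereafter until the last dose at Week 48". The same section describes "a 52-week open-label study period and a 16-week follow-up period" and adds: "The follow-up period consists of a follow-up phone call 20 weeks after the last dose of study drug".

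SAP 5.1 states the purpose: "The Safety Population will be used to perform the 52-week head-to-head safety analysis between the two treatment groups". For the tables, SAP 7.2 says that "The number and percentages of subjects experiencing TEAE will be tabulated" by system organ class and preferred term. Patient-year rates are named for a narrower list: "Summaries (including percentages and event per 100 patient-years) of SAEs, deaths, AEs leading to discontinuation, and Areas of Safety Interest".

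On timing, SAP 6.1 describes a database lock after Week 52, but for efficacy endpoints. SAP 7.1 places the All_RZB safety analysis at study completion. Neither document gives a data cut for the Safety Population tables.

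**The concern.** The 140-day rule is the same in both arms, but it is anchored to the last dose, and the last doses fall 8 weeks apart. The arms are therefore observed for different lengths of calendar time in a comparison labelled as 52 weeks. SAP 7.2 sets no Week 52 limit for a subject who takes no extra dose.

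A crude percentage of subjects with at least one event can only rise as the window lengthens. With equal true risks, the planned tables could show somewhat more TEAEs on secukinumab. The tilt has one direction, favours the sponsor's product, does not shrink with sample size, and acts on most rows of the table at once. The study is open-label and safety is part of its main objective, so readers will compare these columns.

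The stakes are limited. Safety is descriptive, with no hypothesis or alpha attached, and the most important outcomes already get patient-year rates.

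**Working it through.** **Inputs from the documents.** Window 140 days (SAP 7.2); last pre-Week 52 dose at Week 40 on risankizumab and Week 48 on secukinumab (SAP 4.2.1); extra French doses at Weeks 52 and 64 (SAP 4.2.1); 155 subjects per arm (SAP 4.4); 80 sites, 5 of them in France (Protocol synopsis).

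**Assumptions, because the documents give no figures.** TEAE incidence at Week 52 of 2, 5, 10, 50 or 70%; uniform accrual over A weeks; French share of the risankizumab arm equal to its share of sites, 5/80 = 6.25%, all taking the Week 52 dose.

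**1. The plan's own timeline.** 140/7 = 20 weeks. The stated follow-up ends at 52 + 16 = Week 68, which matches secukinumab, 48 + 20 = 68. The 88-week maximum also reproduces: 30/7 + 64 + 20 = 88.3.

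**2. Window ends for subjects who complete dosing.**
- Secukinumab: 48 + 20 = Week 68.
- Risankizumab outside France: 40 + 20 = Week 60, so follow-up past Week 52 is 8 weeks, not 16.
- Risankizumab in France with the extra dose: Week 52.
- Mean on risankizumab: 0.9375 × 60 + 0.0625 × 52 = 59.5 weeks, a gap of 8.5 weeks.

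**3. Mean gap by data cut.** If data are cut when the last subject reaches Week 52, time available past Week 52 is r ~ U(0, A). Windows are 52 + min(16, r) on secukinumab, 52 + min(8, r) on risankizumab outside France, and 52 in France. For A = 26, the gap outside France is (32 + 80)/26 = 4.3 weeks.

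| Cut | Outside France | With France |
|---|---|---|
| Each subject's Week 52 | 0 | 0 |
| Last subject at Week 52, A = 8 | 0 | 0.25 |
| A = 16 | 2.0 | 2.4 |
| A = 26 | 4.3 | 4.7 |
| A = 52 | 6.2 | 6.6 |
| After all follow-up | 8.0 | 8.5 |

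**4. Effect on crude percentages at equal risk.** Let I be the 52-week incidence. With constant hazard, h = −ln(1 − I)/52 and incidence by week t is 1 − exp(−ht). Example at I = 50% with full follow-up: 59.6% at Week 68, 55.1% at Week 60 and 50% at Week 52. Risankizumab is 0.9375 × 55.1 + 0.0625 × 50 = 54.7%, and the difference is 4.86 points before rounding. Two variants are more realistic. One halves capture after Week 52, when the only scheduled contact outside France is a phone call. The other lets risk vary between subjects (gamma frailty, variance 1).

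Difference, secukinumab minus risankizumab, in points (France included):

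| Scenario | 2% | 5% | 10% | 50% | 70% |
|---|---|---|---|---|---|
| Full follow-up, constant hazard | 0.32 | 0.79 | 1.51 | 4.86 | 4.53 |
| Full, halved late capture | 0.16 | 0.40 | 0.77 | 2.62 | 2.58 |
| Full, frailty | 0.32 | 0.76 | 1.41 | 3.32 | 2.58 |
| Full, both | 0.16 | 0.38 | 0.72 | 1.84 | 1.48 |
| A = 26, constant hazard | 0.18 | 0.44 | 0.84 | 2.73 | 2.56 |
| A = 26, halved late capture | 0.09 | 0.22 | 0.43 | 1.47 | 1.45 |
| A = 26, frailty | 0.18 | 0.42 | 0.79 | 1.87 | 1.46 |
| A = 26, both | 0.09 | 0.21 | 0.40 | 1.03 | 0.83 |
| A = 52, constant hazard | 0.25 | 0.61 | 1.18 | 3.80 | 3.55 |
| SE of the difference | 1.59 | 2.48 | 3.41 | 5.68 | 5.21 |

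SE = √(2p(1 − p)/155). The largest difference over all incidences is 4.9 points, near 60%.

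**5. Would patient-year rates alone be enough?** With halved late capture and full follow-up, the observed rate relative to the true rate is (52 + 8)/68 = 0.882 on secukinumab and (52 + 7.5/2)/59.5 = 0.937 on risankizumab. The ratio is 0.94, so secukinumab would read about 6% too low. With a Week 52 lock the ratio is 0.965 (A = 26) or 0.953 (A = 52).

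**6. What a Week 52 truncation leaves.** For subjects who complete dosing, the gap is zero. For early stoppers, with stopping time uniform over 0-52 weeks, the mean gap falls from 3.8 to 2.6 weeks. If 10% stop early in each arm (assumed), that is 0.26 weeks overall, or 0.21 points at 50% incidence and 0.26 at 70%.

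**The case against.** The strongest defence is that a dose-anchored window is conventional and legitimate. It gives every subject the same 20 weeks after the last dose, it matches how events are collected, and secukinumab's later end simply reflects its regimen. That stands, and it is why the 140-day rule should remain the main definition. It does not make calendar time equal under a 52-week label.

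Second, SAP 3.0 and Protocol 7.1 leave detail to a supplement that is not available here. It may already state the cut or add rates. If 52-week means a cut at each subject's Week 52, completers show no distortion. This also stands, and it limits the point to what could happen.

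Third, the effect is small: every figure is below one standard error, all rest on assumed incidences, and the French figures are upper values because some subjects may not take the extra dose. That is fair. A shift in one direction across most rows is still worth removing when removal is cheap.

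Fourth, the remedies are imperfect. With halved late capture and full follow-up, crude incidence on secukinumab is inflated by about 5% in relative terms at 50% incidence (55.1 against 52.4), while the rate is about 6% low. A rate column alone may therefore do no better for common events. A Week 52 truncation leaves 12 weeks after the last risankizumab dose but only 4 after the last secukinumab dose. Both limits are real, which is why the rates and the truncated table should be read together, beside the planned table.

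**Conclusion.** The point holds as a low-priority improvement, not as an error in the plan. The Week 68, Week 60 and Week 52 endpoints follow directly from the SAP's dosing schedule and window rule. The direction is fixed: at equal risk, the longer window can only raise secukinumab's crude percentages.

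The size is not fixed, because the cut is unstated. The mean gap for completers lies between 0 and about 8.5 weeks. With full follow-up, the distortion is about 0.2 to 1.5 points for rows at 2-10% incidence. For any TEAE at 50-70% it is 1.5 to 3.3 points under halved late capture, frailty or both, with an upper bound of 4.9. With a Week 52 lock and 26-week accrual, it is 0.1 to 0.8 points at 2-10% and 0.8 to 1.9 points at 50-70%, with an upper bound of 2.7. Incidence, accrual, late capture, frailty and the French share are all assumptions. Confidence is medium, mainly because the supplement may already settle the matter.

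**What to change.** In SAP 7.2:

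- State the data cut for the Safety Population tables. If the supplement already does so, a cross-reference is enough.
- Add events per 100 patient-years to the overall TEAE table and the table by system organ class and preferred term. Use each subject's actual TEAE window in that table as the denominator.
- Keep the 140-day window as the main definition, and add one supportive head-to-head TEAE table truncated at Week 52, before any additional dose, in both arms.

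The cost is some SAP wording, a rate column and one extra table. Trial conduct, alpha and the efficacy analyses are untouched. The truncated table should carry a note on the unequal time since last dose, and it should not replace the planned one.
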